#### Disease Control Rate (DCR)

DCR is defined as the proportion of participants achieving CR, PR, or SD for  $\geq 6$  months (all per iRANO criteria).

#### Overall Survival (OS)

OS is defined as time from first lerapoltrev infusion to death from any cause, or last follow-up if participant is alive.

**Landmark Survival (LS)**

LS is defined as the proportion of participants alive at  $\geq 6$  and  $\geq 12$  months from time of first lerapoltrev infusion. This will be calculated as survival rate from the OS curve at 6 and 12 months.

**Treatment Period**

Treatment period is defined as the period from catheter placement to Week 104.

**3.3.        TIMING OF ANALYSES**

The final analysis will be completed after the last participant completes or discontinues the study and the resulting clinical database has been cleaned, quality checked, and locked.

**4.            ANALYSIS POPULATIONS**

Data analyses will be based on the efficacy, safety (SAF) and screening analysis sets.

**4.1.        EFFICACY ANALYSIS SET**

The primary efficacy analysis set includes all participants who received at least one dose of lerapoltrev and  $\geq 1$  dose of pembrolizumab. This will be the primary population used for the efficacy analyses. Analyses using the efficacy set will be conducted based on the treatment received.

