### **3.2      Delay in pembrolizumab administration for ongoing peritumoral or cerebral edema (or other TEAE/reasons)**

Peritumoral edema may be associated with PVSRIPO treatment and there is potential for the same after immune checkpoint inhibition. As such, the first planned dose of pembrolizumab (scheduled 2 weeks after PVSRIPO infusion) will be delayed by up to two additional weeks in participants with any ongoing  $\geq$  Grade 3 PTE or CE or  $\geq$  Grade 2 AEs related to PTE or CE following PVSRIPO infusion requiring active treatment, such as new or worsening neurologic signs and symptoms (eg, hemiparesis requiring  $\leq 4$  mg/day dexamethasone or seizure requiring anti-epileptics), until such events resolve to  $\leq$  Grade 1.

If such events have not resolved to  $\leq$  Grade 1 by 4 weeks post-PVSRIPO infusion, or the patient has not received pembrolizumab for any reason by 4 weeks post-PVSRIPO infusion, the participant will not receive pembrolizumab under this trial and will be replaced. If a participant requires  $> 4$  mg/day of dexamethasone or equivalent prior to the first dose of pembrolizumab, the

participant will not receive pembrolizumab under this trial and will also be replaced. These replaced participants will not be considered in the initial DLT assessment of the treatment with PVSRIPO and pembrolizumab.

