#### **4.5 Handling of Withdrawals**

Participants withdrawing from the study prior to receiving PVSRIPO infusion, either voluntarily or due to ineligibility, will be considered non-evaluable in all but the screening analysis set (see **Section 8**); these patients will be replaced. Minimal information will be retained in the study database for screen failures.

Patients who are treated with  $> 4$  mg/day dexamethasone (or equivalent) prior to receiving the first dose of pembrolizumab and patients who do not receive  $\geq 1$  dose of pembrolizumab after PVSRIPO will also be replaced and will not contribute to the PVSRIPO plus pembrolizumab (ie, combination) datasets. These subjects will continue to be followed for safety and efficacy and will be summarized separately.

If patients do not enter the voluntary follow up period, all information as described at the next scheduled study visit if <11 weeks after PVSRIPO treatment or at the End of Study (EOS) visit, should be obtained, if possible and as applicable.

Handling of early withdrawals for analyses are outlined in [Section 8](#).

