## **8.2 Analyzed Population Sets**

All patients enrolled and treated with PVSRIPO will be summarized in all analyses. For any informal summary comparisons of safety or efficacy relative to PVSRIPO alone or pembrolizumab alone from other data sources, both the overall and per-protocol populations may be considered.

A screening analysis set will include all patients who signed the ICF and include screen failures who failed up until PVSRIPO infusion (ie, considered a screen failure if biopsy at time of catheter placement does not confirm rGBM). The safety and efficacy analysis sets are described in **Sections 8.4.5** and **8.4.6**, respectively.

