### 1.1. **STUDY OVERVIEW**

This is an open-label, single-arm, non-randomized study characterizing the efficacy, safety, and tolerability of lerapolturev delivered via intratumoral infusion followed by pembrolizumab in patients with recurrent glioblastoma (rGBM). Approximately 30 eligible participants, 18 years of age or older, are planned to be enrolled and treated with lerapolturev and at least one dose of pembrolizumab in this study. The maximum planned duration of follow-up in this study is up to 24 months (104 weeks), and consists of the following treatments:

- Single lerapolturev infusion on Day 0
  - Note: retreatment with lerapolturev is allowed for qualifying participants who progress  $\geq$  6 months from initial lerapolturev infusion
- Pembrolizumab (200 mg intravenous (IV) infusion) initiated 14 days after lerapolturev infusion (up to 28 days, if necessary), given every 3 weeks, through Week 104 (23.5 months of treatment) or until immune-related AE (irAE) meeting criteria for dose interruption/discontinuation or confirmed progression (must consider clinical and radiographic assessments)

The study will occur in the following periods:

- Screening Period 1: Between 1 and 6 weeks prior to catheter placement
- Screening Period 2: Within 7 days prior to catheter placement
- Catheter Placement and Biopsy (if required) Period: Day 0
- Lerapolturev Infusion Period/Baseline: Single lerapolturev infusion on Day 0 or Day 1 (unless extension granted by Sponsor)
- Post-lerapolturev Infusion, Pembrolizumab Treatment and Follow-up Period: pembrolizumab starting at Week 2 (up to Week 4, max) and every 3 weeks thereafter, to a maximum of Week 104 (approximately 23.5 months maximum pembrolizumab treatment duration)

The study may be adapted or expanded in one or more larger cohorts of participants, in consultation with the Data and Safety Monitoring Board (DSMB), based on interim review and considering the totality of the study data.

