### **Summary Figures**

#### **Efficacy**

- 14.2.1.2 Overall Survival – Kaplan Meier Curve, Safety Set
- 14.2.2.2 Duration of Response – Kaplan Meier Curve, Safety Set

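### Combination-set OS includes 2 to 4 weeks of guaranteed survival, ORR in that set is not like-for-like with 7/61, and the SAP omits the protocol's all-infused and PVSRIPO-only efficacy summaries

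*SAP*

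**What the plan says.** **Who is analysed.** SAP 4.1: "The primary efficacy analysis set includes all participants who received at least one dose of" lerapolturev and at least one of pembrolizumab. SAP 1.1 places the first pembrolizumab dose 14 days after infusion, or up to 28 days if needed.

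**Who drops out of that set.** Protocol 3.2 covers edema-related events not resolved to Grade 1 or less by Week 4, and any patient who "has not received pembrolizumab for any reason by 4 weeks post-PVSRIPO infusion, the participant will not receive pembrolizumab under this trial". A need for more than 4 mg/day dexamethasone before that dose has the same result: "the participant will not receive pembrolizumab under this trial and will be replaced" or equivalent wording. Protocol 4.5 adds that these patients "will not contribute to the PVSRIPO plus pembrolizumab (ie, combination) datasets"; they are followed and summarized separately.

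**Time origin.** SAP 3.2.6: "OS is defined as time from first lerapoltrev infusion to death from any cause". The 6- and 12-month landmark rates are read from that curve.

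**All infused patients.** Protocol 8.2: "All patients enrolled and treated with PVSRIPO will be summarized in all analyses". Protocol 8.4.6 defines a full efficacy set of everyone infused, has PVSRIPO-only patients analysed separately, and names the combination patients as the primary set. SAP 4 has neither an all-infused efficacy set nor a PVSRIPO-only efficacy analysis, and SAP 6 does not list this among its changes.

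**Outputs.** The ORR/DOR table (14.2.1.1) and the OS table (14.2.2.1) use the Efficacy Set. Figures 14.2.1.2 (OS) and 14.2.2.2 (DOR) are both titled "Kaplan Meier Curve, Safety Set". SAP 4.2 defines that set as enrolled participants with a catheter placed.

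**The concern.** Entry to the efficacy set depends on something that happens two to four weeks after the OS clock starts. A patient who dies in that interval is replaced and leaves no trace in the OS table. Nobody in the table can have died before the qualifying dose, and no delayed-entry or landmark correction is planned.

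For ORR, the planning reference is 7 of 61 Phase 1 patients (Protocol synopsis and 8.1; SAP 3.1), the whole cohort described in Protocol 1.2.3, with no condition on reaching a later dose. The estimand in SAP 5.7.1.1 counts death before response as non-response, but a death before pembrolizumab never enters the denominator, and failing to reach pembrolizumab is not listed as an intercurrent event.

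An all-infused or PVSRIPO-only efficacy summary would let a reader see the effect of this selection. Protocol 8 says the SAP governs where the two differ, so its silence removes both. The OS curve and the OS table, as titled, may also describe different patients.

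**Working it through.** **1. The plan's own figure.** Inputs: n = 30, target ORR 31%, two-sided 0.05, reference 11% (SAP 3.1) or 11.5% (Protocol synopsis); 7/61 = 11.475%. Exact binomial:

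- P(X ≥ 7 | 0.11) = 0.0407, above 0.025.
- P(X ≥ 8 | 0.11) = 0.0135 and P(X ≥ 8 | 0.115) = 0.0174, so 8 responses are needed.
- Power = P(X ≥ 8 | 0.31) = 75.7%.

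The stated power above 75% reproduces. The Clopper-Pearson lower limit is 9.9% at 7/30 and 12.3% at 8/30, so 8/30 is also the smallest count whose interval excludes the reference.

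**2. Guaranteed time in OS.** Assumption: exponential survival, S(t) = 2^(−t/m), with median m of 6 to 10 months (the general rGBM range in Protocol 1.1). Day 14 = 14/30.44 = 0.46 months; Day 28 = 0.92 months. Given survival to d, S(t | d) = 2^(−(t−d)/m).

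| m (months) | S(6) from infusion | given alive Day 14 | given alive Day 28 |
|---|---|---|---|
| 6 | 50.0% | 52.7% | 55.6% |
| 8 | 59.5% | 61.9% | 64.4% |
| 10 | 66.0% | 68.1% | 70.3% |

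The 6-month rate rises by 2.1 points (m = 10, Day 14) to 5.6 points (m = 6, Day 28). The 12-month rate rises by about 1 to 3 points; at m = 8, 35.4% becomes 36.8% to 38.3%. The median moves by d itself, 0.46 to 0.92 months. This counts guaranteed survival alone. Selection on edema and steroid need would come on top and cannot be sized from the documents.

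**3. ORR denominator.** Let k be the number infused and replaced. The documents do not give k, so it is an assumption, and all k are taken as non-responders. For 8 responses:

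| k | ORR | exact 95% lower limit |
|---|---|---|
| 0 | 8/30 = 26.7% | 12.28% |
| 2 | 8/32 = 25.0% | 11.46% |
| 3 | 8/33 = 24.2% | 11.09% |
| 5 | 8/35 = 22.9% | 10.4% |

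Against 7/61 = 11.475%, the interval stops excluding the reference at k = 2, by about 0.01 point. Against the SAP's rounded 11%, k = 2 and k = 3 still exclude it.

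On the same assumption, if the all-infused ORR is really 11.5%, the rate in the selected 30 is 0.115 × (30 + k)/30. The chance of 8 or more responses then goes from 0.017 (k = 0) to 0.025 (k = 2), 0.029 (k = 3) and 0.040 (k = 5).

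**4. Direction of the ORR effect.** A patient who dies before Day 28 cannot have a response held for 4 weeks, as the SAP's CR and PR definitions require, and the earliest Phase 1 response came at 5.7 months (Protocol 8.4.6.1). Leaving out early deaths can therefore only raise ORR. For patients replaced for edema, steroid need or administrative delay, the documents give no response data.

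**The case against.** The strongest reply is that the SAP's primary set is the protocol's own. Protocol 8.4.6 names the combination patients as primary and separates the PVSRIPO-only patients, and the objectives are framed after at least one pembrolizumab dose. ORR in that set is a valid estimate for patients who start the combination. This stands: the SAP did not change the primary set, and Protocol 8.2, read with 8.4.6, promised separate summaries rather than a pooled ORR. What the SAP lost is the full set and the separate summary.

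A reader might infer more than the documents support:

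- *That OS is shown only for pembrolizumab-treated patients.* The OS figure is titled on the Safety Set, which is not conditioned on pembrolizumab. The table and figure conflict and must be reconciled.
- *That OS is inflated against a Phase 1 benchmark.* 7/61 is an ORR reference. No OS benchmark or test is planned, Phase 1 survival is background, and external comparisons are described as informal.
- *That a positive ORR would be overturned.* The SAP plans an exact interval, not a formal test. The change at k = 2 depends on an assumed count, on 11.475% rather than 11%, and on 30 patients, although SAP 6 says the full sample was not enrolled.
- *That early toxicity disappears.* The Safety Set keeps enrolled patients with a catheter whether or not they reached pembrolizumab.
- *That the Safety Set certainly includes never-infused patients.* Table 1, footnote 2, calls them screen failures, while SAP 4.2 asks for enrolment and a catheter. Their status is unclear.

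The OS calculation also applies a general rGBM median to patients with KPS of at least 70 and no impending herniation. Their hazard in the first month may be lower, which would shrink the gain.

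**Conclusion.** The point holds and should be fixed, but it does not invalidate the primary set.

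- **OS.** The guaranteed time follows from the definitions and needs no assumption. Its size does: about 2 to 6 points at 6 months under a constant hazard and a 6 to 10 month median, and less if few patients die in the first four weeks.
- **ORR.** The estimate is sound for patients who start the combination. It is not comparable with 7/61 of all infused patients. It is likely to be higher than an all-infused rate, but the documents do not show this, and any shift is illustrative while the number replaced is unknown.
- **Missing analyses.** The full efficacy set and the PVSRIPO-only efficacy summary are absent from the SAP and not declared in Section 6.
- **Outputs.** The sets named for the OS and DOR figures conflict with those of their tables.

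**What to change.** 1. Keep the combination set as primary. Add to SAP 4.1 a supportive set of all participants with at least one lerapolturev infusion, and report ORR, DCR and OS in it. Base any statement against 7/61 on this set.
2. Report the number of replaced patients, the reasons, and their response and survival. This restores the separate summary in Protocol 8.4.6.
3. For combination-set OS, keep infusion as the origin but let patients enter the risk set at first pembrolizumab, or use a Day-28 landmark. Label the result as conditional on survival to the earliest entry time or the landmark; only the all-infused analysis gives survival from infusion without that condition. Moving the origin outright to pembrolizumab is not needed and would depart from the protocol's definition.
4. Give Figures 14.2.1.2 and 14.2.2.2 the sets used by their tables, and add an all-infused OS curve.
5. Record the changes from Protocol 8.2 and 8.4.6 in SAP 6.

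The cost is SAP text and one more run of the same programs; PVSRIPO-only patients are already followed. The reported figures may look slightly less favourable, and early risk sets under delayed entry will be small.

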**4.2.        SAFETY ANALYSIS SET**

The SAF includes all enrolled participants who had an infusion catheter placed. This will be the primary population used for the safety analyses. Participants in the SAF set will be analyzed based on the treatment received.

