#### **8.4.5 Safety Analysis**

The full safety analysis set will include all patients who were administered at least one dose of the PVSRIPO. The safety of study-required pre-infusion procedures including catheter placement, will also be summarized.

Separate summaries will be prepared for the primary safety analysis set, which is patients who received PVSRIPO and  $\geq 1$  dose of pembrolizumab. Patients who received PVSRIPO alone will be summarized separately (secondary safety analysis).

Summaries of TEAE will begin at the time of PVSRIPO infusion. Adverse events considered related to screening or other pre-infusion procedures that are not SOC (eg, PV booster, biopsy prior to infusion, catheter placement without PVSRIPO infusion) will be summarized separately (screening data set).

All safety endpoints for patients receiving PVSRIPO and  $\geq 1$  dose of pembrolizumab may be summarized overall and by the number of pembrolizumab treatments received while on study (eg, 1, 2 to 3, 4 to 6, etc.).

Adverse events will be summarized by highest grade per patient and by attribution according to CTCAE v5.0, using the latest version of MedDRA preferred term as event category and MedDRA primary system organ class body term as Body System category. Unless otherwise stated, adverse events will be displayed in terms of frequency tables by treatment group by decreasing frequency. Each patient will be counted only once within each preferred term or system organ class. If a patient experiences more than one AE (or laboratory value) within a preferred term or system organ class for the same recording period, only the AE with the strongest relationship or the worst severity, as appropriate, will be included in the summaries of relationship and severity.

Events meeting the criteria for a DLT or SAE, leading to discontinuation, resulting in death, etc., will be reported in additional summaries. Changes from baseline over time and abnormal laboratory values, vital signs and NANO and KPS will also be reported.

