## 2. OBJECTIVES

Objective	Endpoint
Primary	
• Anti-tumor activity	• Objective response rate (ORR) • Duration of response (DOR)
• Safety/tolerability	• The frequency and severity of treatment-emergent adverse events (TEAEs) via Common Terminology Criteria for Adverse Events (CTCAE) v 5.0 for participants receiving lerapoltrev and at least one dose of pembrolizumab
Secondary	
• Anti-tumor activity	• Disease Control Rate (DCR)
• Survival	• Overall Survival (OS) • Landmark Survival (LS)

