#### Treatment-emergent Adverse Event (TEAE)

A TEAE will be an AE that occurred during the study on or after catheter placement. Additionally, it is assumed that an AE which was reported to have started on Day 1 without an associated onset time occurred on or after catheter placement.

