**5.            STATISTICAL METHODS**

Descriptive statistical methods will be used to summarize the data from this study. Unless stated otherwise, the term “descriptive statistics” refers to number of participants (n), mean, median, standard deviation, minimum and maximum for continuous data and frequencies and percentages for categorical data. Survival endpoints will be analyzed with Kaplan-Meier method and summarized with median, twenty-fifth and seventy-fifth percentiles, and 95% confidence intervals (CI), if applicable.

All data collected during the study will be included in data listings. Unless otherwise noted, the data will be sorted first by treatment, participant, and then by date within each participant number.

All summary tables and figures will be presented by summarizing the overall population.

Analyses will be implemented using SAS® 9.4 or higher (SAS Institute, Cary, North Carolina, USA). The International Conference on Harmonization (ICH) numbering convention, i.e., ICH-E3, will be used for all tables and listings. Upon completion, all SAS® programs will be validated by an independent programmer within the staff of the third-party vendor doing the primary analysis. The validation process will be used to confirm that statistically valid methods have been implemented and that all data transformations and calculations are accurate. Checks will be made to ensure accuracy, consistency with this plan, consistency within tables, and consistency between tables and corresponding data listings. All documents will be verified by the lead statistician to ensure accuracy and consistency of analyses.

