### 5.8.1. Adverse Events

AEs will be mapped to a Medical Dictionary for Regulatory Activities (MedDRA) version 23.1 by system organ class and PT. If a participant experiences multiple events that map to a single PT, the greatest severity and strongest assessment of relation to a study drug will be assigned to the PT for the appropriate summaries. AE severity will be assessed according to the CTCAE version 5. If CTCAE grading does not exist for an AE, the severity of the AE will be graded as mild (1), moderate (2), severe (3), life-threatening (4), or fatal (5).

The number of participants for the following groups will be summarized by overall:

- Any TEAE
- Any TEAE related to a study drug or catheter with sub bullets for TEAEs related to catheter placement, lerapolturev or pembrolizumab
- Any TESAE
- Any TESAE related to a study drug or catheter with sub bullets for TESAEs related to catheter placement, lerapolturev or pembrolizumab
- Any DLTs
- Any AESIs for lerapolturev
- Any irAEs for pembrolizumab
- Any TEAEs leading to discontinuation of study treatment
- Any TEAE with grade  $\geq 3$
- Any TEAE with grade  $\geq 3$  related to study drug or catheter with sub bullets for TEAEs with grade  $\geq 3$  related to catheter placement, lerapolturev or pembrolizumab
- Any Grade 5 TEAEs
- Any Grade 5 TEAEs related to study drug or catheter with sub bullets for Grade 5 TEAEs related to catheter placement, lerapolturev or pembrolizumab

The occurrence of TEAEs and TEAEs related to study drug or catheter will be summarized by PT, system organ class, and severity. All AEs reported will be listed for individual participants showing both verbatim and PT. All AEs that occurred prior to catheter placement will be excluded from the tables but will be included in the listings.

Missing onset dates will be imputed as previously outlined in Section 3.2.3.2 as required to determine TEAEs.

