#### Safety

- 14.3.1.1 Overall Summary of Treatment-Emergent Adverse Events, Safety Set
- 14.3.1.2 Treatment-Emergent Adverse Events by System Organ Class, Preferred Term, and Greatest Severity, Safety Set
- 14.3.1.3 Treatment-Emergent Adverse Events by Preferred Term in Descending Frequency, Safety Set
- 14.3.1.4 Treatment-Emergent Adverse Events Related to Study Drug or Catheter by System Organ Class, Preferred Term, and Greatest Severity, Safety Set
- 14.3.1.5 Treatment-Emergent Adverse Events Related to Study Drug or Catheter by Preferred Term in Descending Frequency, Safety Set
- 14.3.1.6 Treatment-Emergent Serious Adverse Events by System Organ Class, Preferred Term and Greatest Severity, Safety Set
- 14.3.1.7 Treatment-Emergent Serious Adverse Events Related to Study Drug or Catheter by System Organ Class, Preferred Term, and Greatest Severity, Safety Set
- 14.3.1.8 Treatment-Emergent Dose Limiting Toxicities by System Organ Class, Preferred Term and Greatest Severity, Safety Set
- 14.3.1.9 Treatment-Emergent Adverse Events of Special Interest for Lerapoltrev by System Organ Class, Preferred Term, and Greatest Severity, Safety Set
- 14.3.1.10 Treatment-Emergent irAEs for Pembrolizumab by System Organ Class, Preferred Term, and Greatest Severity, Safety Set
- 14.3.1.11 Treatment-Emergent Adverse Events Leading to Discontinuation of Study Treatment by System Organ Class, Preferred Term, and Greatest Severity, Safety Set
- 14.3.4.1 Summary of Grade Shifts in Laboratory Abnormalities – Hematology, Safety Set
- 14.3.4.2 Summary of Grade Shifts in Laboratory Abnormalities – Chemistry, Pancreatic and Thyroid, Safety Set

- 14.3.4.3 Number of Participants with at Least One ALT, AST, or Total Bilirubin Above Upper Limit of the Normal Range Post-Baseline, Safety Set
- 14.3.4.4 Summary of Vital Signs by Visit, Safety Set
- 14.3.4.5 Summary of Karnofsky Performance Status by Visit, Safety Set
- 14.3.4.6 Summary of Neurologic Assessment in Neuro-Oncology Score by Visit, Safety Set

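### No planned table reports the SAP's own primary safety endpoint: all safety tables use the catheter-placed set, summarised overall, and the protocol's separate combination and PVSRIPO-only summaries are dropped without being listed as a change

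*SAP*

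**What the plan says.** The SAP's objectives table (Section 2) gives the primary safety endpoint as the frequency and severity of TEAEs "for participants receiving lerapoltrev and at least one dose of pembrolizumab". SAP Section 4.2 then defines the only safety population: "The SAF includes all enrolled participants who had an infusion catheter placed. This will be the primary population used for the safety analyses". Membership requires neither infusion nor pembrolizumab. The same section adds: "Participants in the SAF set will be analyzed based on the treatment received".

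On display, SAP Section 5 states: "All summary tables and figures will be presented by summarizing the overall population". Section 5.8.1 introduces the adverse event counts with "The number of participants for the following groups will be summarized by overall". In Section 10 every 14.3.x table carries the Safety Set label, including "Treatment-Emergent irAEs for Pembrolizumab by System Organ Class, Preferred Term, and Greatest Severity, Safety Set".

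The protocol is organised differently. Section 8.4.5 has a full safety set of everyone dosed with PVSRIPO, and then: "Separate summaries will be prepared for the primary safety analysis set, which is patients who received PVSRIPO and" at least one dose of pembrolizumab. It also summarises PVSRIPO-only patients separately, as the secondary safety analysis (listed as an endpoint in Section 2.1.2). Sections 7.1.3 and 8.4.5 start TEAEs at infusion and report events from catheter placement without infusion separately. The SAP moves the start: "A TEAE will be an AE that occurred during the study on or after catheter placement".

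SAP Section 6 lists the changes to the planned analyses. It mentions neither the safety summaries nor the TEAE start. Under Protocol Section 8, the SAP governs where the two documents differ.

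**The concern.** Safety of the combination is a primary objective, and its endpoint is tied to a specific exposed population. If every table is built on a wider set with no split by exposure, the report will contain no direct statement of that endpoint. Participants who never had pembrolizumab would count in the denominator for pembrolizumab immune-related events. For events that either agent, the procedure or the disease can cause, their events would be mixed with those of combination participants. The protocol's secondary safety endpoint would have no table. Because the SAP prevails and Section 6 is silent, a reader of the report would not know that these summaries had been planned and removed.

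**Working it through.** The plan states no safety rate or precision figure, so there is nothing to reproduce. The check compares the texts and then works out how pooling acts.

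**1. Does any planned table use the endpoint population?** SAP Section 4 names three kinds of set: efficacy, safety and screening. Only the efficacy set (4.1) requires lerapolturev plus at least one pembrolizumab dose, and no 14.3.x table uses it.

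**2. Is the safety set split by exposure inside the tables?** Section 4.2 refers to treatment received, but no treatment groups are defined. Sections 5 and 5.8.1 ask for overall summaries. The sort by treatment in Section 5 applies to listings. The catheter, lerapolturev and pembrolizumab sub-rows in Section 5.8.1 classify related events by attribution; they do not divide participants by exposure.

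**3. Can the safety set hold participants without pembrolizumab?** Yes. The protocol synopsis and Section 3.2 keep PVSRIPO-only patients in follow-up and replace them. SAP Section 5.6 summarises pembrolizumab exposure with a 0-cycle category, and that table (14.1.5.1) is on the Safety Set. The plan allows for such participants; it does not show how many there are.

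**4. Does it hold participants who were never infused?** The wording is unclear. Under Protocol 5.2.1 the catheter may be placed before the diagnosis is confirmed and removed without infusion. SAP Table 1, footnote 2 makes an uninfused patient a screen failure. SAP 4.3 places in the screening set those who failed up to catheter placement, with an unconfirmed biopsy at placement as its example. SAP 4.2 admits enrolled participants with a catheter, and the SAP does not define enrolled.

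**5. Effect on pembrolizumab immune-related events.** Let N be combination participants and K the others in the set. Only the N can contribute such an event, so with x participants affected:

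pooled rate = x/(N+K) = (x/N) × N/(N+K)

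N and K are assumed here:

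| N | K | N/(N+K) | 10 affected participants: x/N → pooled |
|---|---|---|---|
| 30 | 0 | 1.00 | 33.3% → 33.3% |
| 30 | 3 | 30/33 = 0.91 | 33.3% → 30.3% |
| 30 | 6 | 30/36 = 0.83 | 33.3% → 27.8% |
| 20 | 6 | 20/26 = 0.77 | 50.0% → 38.5% |

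The last row is included because SAP Section 6 says the full sample was not enrolled, so N is below plan by an unstated amount.

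**6. Effect on other TEAEs.** With rate p_c on the combination and p_o in the others:

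shift = K/(N+K) × (p_o − p_c)

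For N=30 and K=6 the weight is 6/36 = 16.7%. Assumed rates of 50% and 20% give 50 − 5.0 = 45.0%. Assumed rates of 30% and 60% give 30 + 5.0 = 35.0%. The direction depends on the event.

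**7. TEAE start.** Protocol 5.2.2 puts infusion on the day of placement or the next day, and up to 72 h after placement by exception. Events in that window are TEAEs under the SAP and not under Protocol 7.1.3 and 8.4.5. SAP 3.2.3.1 also imputes a missing relationship to study drug as definite for any event from catheter placement on, which includes this window.

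**The case against.** The strongest reply is that the information is not lost. SAP 5.1 reports the size of each analysis population, and the efficacy set in SAP 4.1 is exactly the combination population. For pembrolizumab immune-related events the numerator is the same in either set, so the undiluted rate is one division away. Other TEAEs can be rebuilt from the analysis-set, pembrolizumab infusion and adverse event listings. This stands. A reader might infer that combination safety cannot be recovered from the planned output at all, and the documents do not support that. What is missing is a planned table of a primary endpoint, and rebuilding it by hand from listings is not a substitute.

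Pooling as such is not a departure either. Protocol 8.4.5 has its own full safety set of all PVSRIPO-treated patients, and Protocol 8.2 wants all of them summarised. The defect is that the separate summaries were not carried over.

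Two further inferences go too far:

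- That never-infused patients are certainly in the set. Step 4 shows only an ambiguity.
- That biopsy events generally become TEAEs. Biopsy precedes catheter placement (Protocol 5.2.1), and SAP 5.8.1 excludes events before placement from the tables. The exceptions are later-onset events and Day 1 events with no recorded time. Related events are also broken out by attribution to the catheter, so counting from placement is a defensible, inclusive choice if it is declared.

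**Conclusion.** The mismatch is established from the text alone: the SAP defines a primary safety endpoint that no planned table reports on its own population. The protocol's separate combination and PVSRIPO-only safety summaries are dropped without a record in SAP Section 6.

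Its numerical effect is unknown. It depends on N and K, which the documents do not give. The factors 0.91 and 0.83 assume 30 combination participants and an invented K, so they illustrate the mechanism and do not give a range for this trial. If K is 0, the populations coincide and only the TEAE start remains to be reconciled, over a short window.

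The safety analysis is descriptive, with no test or threshold attached to these denominators. The dose-limiting toxicity decision rests on the first three to six combination-treated patients (Protocol 3.1), not on these tables. The point should be fixed before the tables are run, but it does not undermine a decision rule.

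**What to change.** 1. In SAP 4.2, name the population of SAP 4.1 (lerapolturev plus at least one pembrolizumab dose) as the primary safety set and use it for the 14.3.1.x tables.
2. In the same tables, show lerapolturev-only participants in their own column, and any catheter-only participants in another. Keep the catheter-placed set as a supportive total. Amend the overall-only statements in Sections 5 and 5.8.1 to match.
3. State whether a participant with a catheter but no infusion is enrolled and in the safety set, or a screen failure, so that SAP 4.2, 4.3 and Table 1 footnote 2 agree.
4. Reconcile the TEAE start. Either start at infusion and tabulate events between placement and infusion separately, or keep catheter placement and record the change in Section 6.
5. If any separate summary is dropped on purpose, including the PVSRIPO-only secondary endpoint, list it in Section 6 with the reason.

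The cost is SAP wording and extra columns. The combination population is already defined for efficacy, the exposure and onset data are already collected, and no new data are needed.
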